### **7.9.2.3 Potential Predictive Relationship of PD-L1 Status for Efficacy Measures**

Analyses will be performed using all evaluable PD-L1 subjects, if not otherwise specified.

#### **Analyses for ORR per BICR:**

A logistic regression model will be fitted for ORR with treatment, PD-L1 status, and treatment by PD-L1 status interaction. Although the study is not designed to have appropriate power to formally test the interaction of the model, an interaction test at significance level of 0.2 will warrant further exploration and the following statistics will be reported:

- Interaction p-value
- Odds ratio of nivolumab/ipilimumab vs nivolumab/ipilimumab-placebo and its associated 95% CI for each PD-L1 status subgroup
- Odds ratio of PD-L1  $\geq$  X% vs.  $<$  X% and its associated 95% CI within each treatment group where X denotes the PD-L1 expression cut-off.

#### **Analyses for PFS per BICR:**

A Cox proportional hazards regression model will be fitted for PFS with treatment, PD-L1 status, and treatment by PD-L1 status interaction. Although the study is not designed to have appropriate power to formally test the interaction of the model, an interaction test at significance level of 0.2 will warrant further exploration and the following statistics will be reported:

- Interaction p-value
- Hazard ratio of nivolumab/ipilimumab vs nivolumab/ipilimumab-placebo and its associated 95% CI for each PD-L1 status subgroup
- Hazard ratio PD-L1  $\geq$  X% vs.  $<$  X% and its associated 95% CI within each treatment group where X denotes the PD-L1 expression cut-off.

This analysis will be conducted using primary definition of PFS.

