#### 7.5.1.1 Primary Analysis of ORR

The comparison of ORR between nivolumab in combination with ipilimumab vs nivolumab in combination with ipilimumab placebo in platinum refractory randomized subjects will be carried out using a two-sided Cochran-Mantel-Haenszel (CMH) test stratified by the stratification factors PD-L1 status (expressing vs non-expressing/non-evaluable/indeterminate) and HPV p-16 status (oropharyngeal HPV p16 positive (including unknown primary with HPV p16 positive) vs oropharyngeal HPV p16 negative or nonoropharyngeal) as recorded in the IVRS. The significance level will be adjusted for an interim analysis which will be performed when around 70% of platinum-refractory subjects have been followed for at least 6 months after randomization. Using Lan-DeMets alpha spending function with O'Brien-Fleming boundaries, the significance level for this comparison will be determined by the fraction of subjects included in the interim analysis. If the analysis is performed when exactly 70% of platinum refractory subjects have reached 6 months follow up after randomization, the alpha level is 0.015 for the interim and 0.045 for the final. An associated odds ratio (nivolumab/ipilimumab vs. nivolumab/ipilimumab placebo) and corresponding CI will be calculated. ORR will be summarized by a binomial response rate and its corresponding two-sided exact CI using Clopper-Pearson method for each treatment group. An estimate of the difference in ORRs between arms (nivolumab/ipilimumab vs. nivolumab/ipilimumab placebo) and corresponding CI will be calculated using Cochran-Mantel-Haenszel (CMH) methodology and adjusted by the stratification factors as recorded in the IVRS.

The formula is

$$\hat{\theta} = \frac{\sum_i w_i \hat{\theta}_i}{\sum_i w_i} \sim N \left[ \theta, \frac{\sum_i w_i^2 \left[ \frac{p_{ix}(1-p_{ix})}{n_{ix}-1} + \frac{p_{iy}(1-p_{iy})}{n_{iy}-1} \right]}{\left( \sum_i w_i \right)^2} \right]$$

where  $\hat{\theta} = p_{ix} - p_{iy}$  is the difference in rates in the *i*th stratum,  $w_i = \frac{n_{ix}n_{iy}}{n_{ix} + n_{iy}}$ , and  $n_{ix}$  and  $n_{iy}$  are the number of subjects randomized to treatments x and y, respectively, in the *i*th stratum.

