### **7.5.3 Progression Free Survival**

#### **7.5.3.1 PFS primary analysis**

The PFS function based on BICR assessment for each treatment arm will be estimated using Kaplan Meier technique and will be displayed graphically in the platinum refractory and platinum eligible subgroups, separately. The primary definition of PFS will be used in this analysis ([Section 4.2.2](#)). Median Survival time along with 95% CI will be constructed based on a log-log transformed CI for the survivor function. The hazard ratio and the 95% confidence interval will be estimated in a stratified Cox proportional hazards model using the randomized arm as a single covariate, stratified by PD-L1 status and HPV p-16 status, in the platinum refractory and platinum eligible subgroups, separately. PFS rates at 3, 6, 12 and 24 months, with 95% CIs will be estimated using Kaplan-Meier methodology. Minimum follow-up must be greater than or equal to the time-point to generate the rate.

The source of PFS event as assessed by BICR (RECIST 1.1 progression or death) will be summarized by treatment group.

The status of subjects who are censored (as per primary definition of PFS) in the PFS KM analysis will be tabulated for each randomized treatment group using the following categories:

- On-study (on-treatment, follow-up)
- Off-study (lost to follow-up, withdrawn consent, never treated)
- Received subsequent anticancer therapy

- No baseline tumor assessment

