### **7.9.2.2 Association Between PD-L1 Status and Efficacy Measures**

#### **Analyses for ORR per BICR endpoint:**

Evaluation of association between PD-L1+ tumor expression level and ORR in subjects treated with nivolumab/ipilimumab and nivolumab/ipilimumab-placebo

- A separate logistic regression model will be fitted for ORR with PD-L1+ expression level as a sole covariate for subjects treated with nivolumab/ipilimumab vs nivolumab/ipilimumab-placebo, respectively. An appropriate transformation of PD-L1+ expression may be considered depending on an assessment of fit of the model. The following summaries will be presented by treatment arm:
  - Odds ratios corresponding to a 1 and 10% PD-L1 expression change and its associated 95% CI, respectively
  - A plot of estimated response probability with 95% confidence band vs PD-L1+ expression (X-axis)
  - A plot of estimated response probability for each treatment arm in a single plot vs PD-L1+ expression (X-axis)
- Box plot of PD-L1 expression versus Response Status
- Receiver Operating Characteristics (ROC) analysis with ORR will be performed to help assess in-study (re-substitution) predictive accuracy of the logistic regression model and whether there is a clinically meaningful threshold of PD-L1 expression. The following summaries will be provided for treated subjects by treatment arm:
  - A plot of the ROC curve
  - A plot of estimated true positive fraction and false positive fraction vs. PD-L1+ expression (X-axis)

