#### **Analyses for OS endpoint:**

A Cox proportional hazards regression model will be fitted for OS with treatment, PD-L1 status, and treatment by PD-L1 status interaction. Although the study is not designed to have appropriate

power to formally test the interaction of the model, an interaction test at significance level of 0.2 will warrant further exploration and the following statistics will be reported.

- Interaction p-value
- Hazard ratio of nivolumab/ipilimumab vs nivolumab/ipilimumab-placebo and its associated 95% CI for each PD-L1 status subgroup
- Hazard ratio PD-L1  $\geq X\%$  vs.  $< X\%$  and its associated 95% CI within each treatment group where X denotes the PD-L1 expression cut-off.

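### The exploratory PD-L1 models in SAP 7.9.2.3 omit platinum status and HPV p-16, so their PD-L1 ratios and interaction may partly reflect those factors; adjusted results alongside would be a minor improvement

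*SAP*

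**What the plan says.** SAP 7.9.2.3 sets out three models. For ORR: "A logistic regression model will be fitted for ORR with treatment, PD-L1 status, and treatment by PD-L1 status interaction". For PFS: "A Cox proportional hazards regression model will be fitted for PFS with treatment, PD-L1 status, and treatment by PD-L1 status interaction". For OS: "A Cox proportional hazards regression model will be fitted for OS with treatment, PD-L1 status, and treatment by PD-L1 status interaction". The population rule is "Analyses will be performed using all evaluable PD-L1 subjects, if not otherwise specified". Each model gives an interaction p-value (a result at the 0.2 level prompts further exploration), the treatment odds or hazard ratio in each PD-L1 group, and the ratio for PD-L1 at or above versus below the cut-off with "its associated 95% CI within each treatment group where X denotes the PD-L1 expression cut-off".

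SAP 2.2 lists three randomisation factors: platinum status, PD-L1 status and HPV p-16. The first and third appear in none of these models. The default in SAP 7.1 concerns a treatment hazard ratio from an IVRS-stratified Cox model in which treatment is the only covariate. It does not reach the logistic model or the PD-L1 ratios.

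The main analyses do use these factors. The primary ORR comparison, in the refractory cohort, is a Cochran-Mantel-Haenszel "test stratified by the stratification factors PD-L1 status (expressing vs non-expressing/non-evaluable/indeterminate) and HPV p-16 status". The PFS hazard ratio is "stratified by PD-L1 status and HPV p-16 status, in the platinum refractory and platinum eligible subgroups, separately", and OS (7.5.4.1) is handled likewise. Unadjusted PD-L1 associations are already in 7.9.2.2, for example: "A separate logistic regression model will be fitted for ORR with PD-L1+ expression level as a sole covariate".

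**The concern.** PD-L1 status is not assigned at random. Two consequences follow if it is associated with HPV p-16 or platinum status.

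First, the PD-L1 ratio within an arm compares groups with a different HPV p-16 mix, and in an overall fit a different platinum mix. It then combines the PD-L1 association with the prognostic effect of those factors.

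Second, if either factor also modifies the treatment effect, the two PD-L1 groups show different treatment effects even when PD-L1 has no part in it. Adding the factor as a main effect or stratum corrects for prognosis but not for effect modification.

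At stake is the interpretation of a biomarker analysis. Efficacy by PD-L1 is a listed secondary objective (SAP 3.2), but these models are not formally powered and no decision rests on them.

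**Working it through.** **Inputs from the documents.** Cohorts 216 and 180; allocation 2:1; ORR 35% versus 15%. The plan's odds ratio reproduces: (0.35/0.65)/(0.15/0.85) = 0.5385/0.1765 = 3.051. The plan gives no figure for the 7.9.2.3 models.

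**Assumptions.** The documents give no PD-L1 or HPV p-16 prevalences and no prognostic strengths. Unless stated: HPV+ 20% of refractory and 30% of eligible subjects; conditional PD-L1 odds ratio 1.50, equal in both arms; response 15% in the reference cell (eligible, HPV-, PD-L1-, control); HPV odds ratio 2; refractory odds ratio 1/1.5.

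**Formula.** logit(response) = b0 + bT·T + bP·P + bTP·T·P. The PD-L1 odds ratio is exp(bP) in control and exp(bP + bTP) in combination. The interaction is the ratio of odds ratios, exp(bTP).

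**Worked case, refractory cohort alone.** PD-L1+ is 80% in HPV+ and 55% in HPV-. The treatment odds ratio is 3.051 in HPV- and 1.0 in HPV+. The true PD-L1 interaction is 1.00.

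- HPV+ share among PD-L1+: 0.16/(0.16 + 0.44) = 0.267. Among PD-L1-: 0.04/(0.04 + 0.36) = 0.10.
- Control, PD-L1-: 0.90 × 0.1053 + 0.10 × 0.1905 = 0.1138, odds 0.1284.
- Control, PD-L1+: 0.733 × 0.15 + 0.267 × 0.2609 = 0.1796, odds 0.2189.
- Combination, PD-L1-: 0.90 × 0.2642 + 0.10 × 0.1905 = 0.2568, odds 0.3455.
- Combination, PD-L1+: 0.733 × 0.35 + 0.267 × 0.2609 = 0.3262, odds 0.4842.
- Treatment odds ratio: 0.3455/0.1284 = 2.69 in PD-L1- and 0.4842/0.2189 = 2.21 in PD-L1+. Ratio 0.82.

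Both treatment odds ratios are genuine randomised effects; they differ only through the HPV mix. Adding HPV p-16 as a covariate leaves 0.82. Adding treatment-by-HPV gives 1.00.

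**Within-arm PD-L1 odds ratio, overall fit, equal treatment effects (large-sample limits; true 1.50).**

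| Setting | Control | Combination | Both factors added |
|---|---|---|---|
| PD-L1 unrelated to either factor | 1.46–1.49 | 1.45–1.48 | 1.50 |
| PD-L1 related to HPV (70% vs 60%, to 80% vs 55% with HPV odds ratio 3 and refractory 1/2) | 1.59–1.91 | 1.57–1.83 | 1.50 |
| PD-L1 related to platinum (70% refractory, 55% eligible) | 1.38 | 1.37 | 1.50 |

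The first row is non-collapsibility only; its upper setting also uses HPV odds ratio 3 and refractory 1/2. The largest log shift is ln(1.91/1.50) = 0.24, against a standard error of 0.49.

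**Ratio of odds ratios, overall fit (true 1.00).**

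| Treatment effect varies by | As written | Main effects added | Matching treatment-by-factor term added |
|---|---|---|---|
| Platinum (3.051 refractory, 1.0 eligible; PD-L1+ 70% vs 55%) | 1.18 | 1.19 | 1.00 |
| Same, prevalences reversed | 0.84 | 0.84 | 1.00 |
| HPV (3.051 HPV-, 1.0 HPV+; PD-L1+ 80% in HPV+, 55% in HPV-) | 0.80 | 0.80 | 1.00 |

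In the HPV row, a treatment-by-platinum term alone still leaves 0.80. A harsher setting lets both factors modify treatment (odds ratio × 1/3 in eligible, × 1/2 in HPV+; no PD-L1 effect; prognostic odds ratios 1.8; PD-L1+ 45% refractory and 65% eligible; HPV+ 35% of PD-L1+ and 15% of PD-L1-). It gives 0.70, 0.70 and, with both terms, 1.00. If the factors are prognostic only, the ratio in that setting is 0.99.

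**Chance of a false flag.** With z = ln(ratio)/SE, P(p < 0.2) = Φ(z − 1.2816) + Φ(−z − 1.2816). For 1.18 with SE 0.56, z = 0.30 and P = 22%. For the 0.70 setting it is 31%. The nominal value is 20%.

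**Cox, simulated (600,000 per setting; assumed treatment hazard ratio 0.70 unless stated).** A true within-arm PD-L1 hazard ratio of 0.80 appears as 0.71–0.78 (HPV-related) or 0.87 (platinum-related), and as 0.80–0.81 when stratified. The largest log shift is 0.12, against a standard error of 0.21–0.22. With treatment hazard ratio 0.60 in refractory and 1.00 in eligible, the ratio of hazard ratios is 0.92 as written, 0.92 stratified and 1.00 with treatment-by-platinum.

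Standard errors assume all 396 are evaluable. At the 20% cap on non-evaluable or indeterminate results they grow by 1/√0.8 = 1.12.

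**The case against.** The strongest reply is that 7.9.2.3 follows a consistent convention. The SAP stratifies its main analyses and leaves subset analyses unadjusted: unweighted ORR differences in 7.5.1.3 and unstratified OS hazard ratios in 7.5.4.3. A marker can be predictive without acting independently of HPV p-16 or platinum status, and the SAP does not claim to estimate an independent PD-L1 effect. Randomisation was stratified on all three factors, so the treatment effect in each PD-L1 group is protected. Protocol 8.4.2 and SAP 3.2 and 7.5 call for results by platinum cohort as well as overall, and platinum cannot confound within a cohort. The SAP itself says the study is not designed to power the interaction test.

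All of this stands, and it limits the point to a minor improvement. What remains is that by-cohort fits still omit HPV p-16, that an overall fit is foreseen, and that unadjusted within-arm associations are already supplied by 7.9.2.2.

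A reader might infer that the models pool the cohorts with no by-cohort rule. The documents do not support that. Text before 7.9.2 and after 7.9.2.4 is redacted, the Section 4.3.6 cited in 6.3 is not visible, and a rule may be there.

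**Conclusion.** A minor improvement to an exploratory analysis, not an error in the plan. The omission is plain in the unredacted model statements. Its effect is conditional. The within-arm ratios shift in substance only if PD-L1 is associated with HPV p-16 or platinum status. The interaction is misattributed only if such a factor also modifies the treatment effect, and either factor can do this.

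Size and direction cannot be known from the documents. In the settings tried, the shifts stay below their standard errors and the false-flag rate rises from 20% to between 22% and 31%.

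A reader might go further and infer that the treatment effects by PD-L1 group are biased. They are not. With equal effects across cohorts and HPV groups they read 2.76–2.97 as written against 3.05 adjusted, which reflects non-collapsibility and not confounding. The primary comparison, sample size and alpha are untouched.

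**What to change.** In SAP 7.9.2.3, report adjusted results next to the unadjusted ones.

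- Within each platinum cohort: stratify the Cox models by IVRS HPV p-16 and add HPV p-16 as a covariate to the logistic model.
- Overall fit: do the same with both platinum status and HPV p-16.
- Sensitivity analysis of the interaction: add treatment-by-HPV p-16 in every fit and treatment-by-platinum in the overall fit. Then report the treatment effect by PD-L1 status per cohort, or standardised over these factors, because the treatment coefficient alone then refers to one reference group.

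If redacted text already sets a by-cohort rule, only the covariates, strata and extra terms need adding.

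The cost is SAP wording and programming, since the factors are already in IVRS. Intervals widen slightly: the illustrative standard error of the log ratio of odds ratios goes from 0.56 to 0.58 overall. By-cohort ORR fits are imprecise (about 0.8 to 0.9; 72 × 0.15 ≈ 11 expected control responders in the refractory cohort) and should be read as descriptive.

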#### **Analyses for OS endpoint:**

A Cox proportional hazards regression model will be fitted for OS with treatment, PD-L1 status, and treatment by PD-L1 status interaction. Although the study is not designed to have appropriate

power to formally test the interaction of the model, an interaction test at significance level of 0.2 will warrant further exploration and the following statistics will be reported.

- Interaction p-value
- Hazard ratio of nivolumab/ipilimumab vs nivolumab/ipilimumab-placebo and its associated 95% CI for each PD-L1 status subgroup
- Hazard ratio PD-L1  $\geq X\%$  vs.  $< X\%$  and its associated 95% CI within each treatment group where X denotes the PD-L1 expression cut-off.

#### **7.9.2.4 Association Between PD-L1 Status and select AE**

Select AEs will be summarized by worst CTC Grade by treatment group for

- Each PD-L1 status subgroup by 1% cut-off (positive, negative)
- PD-L1 not evaluable or indeterminate subgroup

[REDACTED]

[REDACTED]

[REDACTED]

[REDACTED]

[REDACTED]

[REDACTED]

[REDACTED]

[REDACTED]

[REDACTED]

[REDACTED]

[REDACTED]

[REDACTED]

[REDACTED]

[REDACTED]

[REDACTED]

[REDACTED]

[REDACTED]

## 8 CONVENTIONS

The following conventions may be used for imputing partial dates for analyses requiring dates:

For missing and partial adverse event onset dates, imputation will be performed using the Adverse Event Domain Requirements Specification. Missing and partial Non-Study Medication Domain dates will be imputed using the derivation algorithm described in 4.3.3 of BMS Non-Study Medication Domain Requirements Specification.

For death dates, the following conventions will be used for imputing partial dates:

- If only the day of the month is missing, the 1st of the month will be used to replace the missing day. The imputed date will be compared to the last known date alive day and the maximum will be considered as the death date.
- If the month or the year is missing, the death date will be imputed as the last known date alive day
- If the date is completely missing but the reason for death is present the death date will be imputed as the last known date alive day

For date of progression, the following conventions will be used for imputing partial dates:

- If only the day of the month is missing, the 1st of the month will be used to replace the missing day\*.
- If the day and month are missing or a date is completely missing, it will be considered as missing.

\*In cases where the date of death is present and complete, the imputed progression date will be compared to the date of death. The minimum of the imputed progression date and date of death will be considered as the date of progression.

For other partial/missing dates, the following conventions may be used:

- If only the day of the month is missing, the 15th of the month will be used to replace the missing day.
- If both the day and the month are missing, “July 1” will be used to replace the missing information.
- If a date is completely missing, it will be considered as missing.

The following conversion factors will be used to convert days to months or years: 1 month = 30.4375 days and 1 year = 365.25 days.

Duration (e.g. time from first diagnosis to first dosing date, duration of response, and time to response) will be calculated as follows:

$$\text{Duration} = (\text{Last date} - \text{first date} + 1)$$

All statistical analyses will be carried out using SAS (Statistical Analysis System software, SAS Institute, North Carolina, USA) unless otherwise noted.

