#### **3.7.2 Lost to Follow-Up**

All reasonable efforts must be made to locate subjects to determine and report their ongoing status. This includes follow-up with persons authorized by the subject as noted above. Lost to follow-up is defined by the inability to reach the subject after a minimum of three documented phone calls, faxes, or emails as well as lack of response by subject to one registered mail letter. All attempts should be documented in the subject's medical records. If it is determined that the subject has died, the site will use permissible local methods to obtain the date and cause of death.

If investigator's use of third-party representative to assist in the follow-up portion of the study has been included in the subject's informed consent, then the investigator may use a Sponsor-retained third-party representative to assist site staff with obtaining subject's contact information or other

public vital status data necessary to complete the follow-up portion of the study. The site staff and representative will consult publicly available sources, such as public health registries and databases, in order to obtain updated contact information. If after all attempts, the subject remains lost to follow-up, then the last known alive date as determined by the investigator should be reported and documented in the subject's medical records.

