### **4.2.2 Progression-free Survival by BICR**

#### **4.2.2.1 Primary Definition of Progression-free Survival by BICR**

[figure not shown]
The BICR-assessed PFS is defined as the time from randomization to the date of first documented disease progression, as assessed by the BICR using RECIST 1.1 criteria, or death due to any cause, whichever occurs first. Subjects who died without a reported progression will be considered to have progressed on the date of their death. Subjects who did not progress or die will be censored

on the date of their last evaluable tumor assessment. Subjects who did not have any on study tumor assessments and did not die will be censored on the date they were randomized. Subjects who started any subsequent anti-cancer therapy, including tumor-directed radiotherapy and tumor-directed surgery, without a prior reported progression will be censored on the date of their last evaluable tumor assessment prior to/on the initiation of the subsequent anti-cancer therapy.

- For subjects without any baseline TA, they will be censored at randomization date
- For subjects with baseline TA but without any on study TA, if no death information is available, subjects will be censored at randomization date; if death information is available, subjects will be either an event at death date if no subsequent therapy is in the record or censored at randomization date if subsequent therapy exists.
- For subjects with baseline and on-study TA,
  - a) Subjects who did not have disease progression per BICR assessment or die will be censored on the date of last tumor assessment on study if there's no subsequent therapy or last tumor assessment conducted on/prior to the subsequent therapy if there's one.
  - b) Subjects who did have disease progression per BICR assessment or die will be an event at disease progression per BICR assessment or death date if there's no subsequent therapy before the event or censored at the last tumor assessment date conducted on/prior to the subsequent therapy date.

Further explanation for various censoring scenarios for the primary definition of PFS are presented in [Figure 4.2.2.1-1](#).

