### 4.2.3 Overall Survival

OS is defined as the time between the date of randomization and the date of death. For subjects without documentation of death, OS will be censored on the last date the subject was known to be alive. The overall survival rate at time  $T$  is defined as the probability that a subject is alive at time  $T$  following randomization.

[REDACTED]

[REDACTED]

[REDACTED]

[REDACTED]

[REDACTED]

[REDACTED]

[REDACTED]

[REDACTED]

[REDACTED]

[REDACTED]

[REDACTED]

[REDACTED]

[REDACTED]

[REDACTED]

[REDACTED]

[REDACTED]

[REDACTED]

[Redacted]

[Redacted]

[Redacted]

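### SAP 8 ignores a recorded year of death when the month is missing, so OS, PFS or DOR can end in an earlier year than the one on record

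*SAP*

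**What the plan says.** SAP 8 gives three rules for incomplete death dates.

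- Day missing: the first of the recorded month is substituted, and then "The imputed date will be compared to the last known date alive day and the maximum will be considered as the death date".
- Month or year missing: "If the month or the year is missing, the death date will be imputed as the last known date alive day".
- Date wholly missing but a reason for death present: the last known alive date.

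For an incomplete progression date with the day missing, the same section also substitutes the first of the month and, where a complete death date exists, applies a cap: "The minimum of the imputed progression date and date of death will be considered as the date of progression".

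The death date feeds three endpoints. In SAP 4.2.3, "OS is defined as the time between the date of randomization and the date of death". In SAP 4.2.2.1, "Subjects who died without a reported progression will be considered to have progressed on the date of their death". In SAP 4.1.1, death from any cause ends DOR if it comes before progression.

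**The concern.** The second rule treats two different records alike. If the year is missing, the last known alive date is all there is. If the year is known and only the day and month are missing, the record still says the subject was alive until at least 1 January of that year. The rule drops that information. It is the only partial-date rule for death or progression that can contradict what is on file, since the day-missing rule keeps the recorded month and the progression rule is held to a complete death date. No reason is given for the difference.

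At stake is the placing of some OS events, and of PFS and DOR events where death is the event. SAP 7.5.4.1 plans OS rates out to 60 months, and Protocol 3.2 allows survival follow-up for up to 5 years. Protocol 3.7.2 lets lost subjects be traced: "The site staff and representative will consult publicly available sources, such as public health registries and databases". A subject traced in this way could have an old last contact and an incomplete death date.

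**Working it through.** No figure in the plan depends on this rule, so there is none to reproduce. The check applies the rules literally to assumed dates and then averages over assumed gaps.

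**Inputs from the documents.** The death-date rules, 30.4375 days per month, and duration = last date − first date + 1 (all SAP 8; the duration formula is taken to cover OS). Survival contact about every 3 months, ± 7 days (Protocol 3.7). **Assumed:** randomization on 15 Jan 2018, and the last-contact dates below.

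**1. One death under two rules.** Last known alive 15 Nov 2018.
- Recorded as Jan 2019, day missing: later of 1 Jan 2019 and 15 Nov 2018 = 1 Jan 2019.
- Recorded as 2019, month missing: 15 Nov 2018, a year too early on the calendar.

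**2. Death recorded only as 2019.** The alternative is the later of 1 Jan 2019 and the last known alive date.

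| Last known alive | SAP death date | Alternative | Difference, days | OS, SAP rule (months) | OS, alternative (months) |
|---|---|---|---|---|---|
| 20 Dec 2018 | 20 Dec 2018 | 1 Jan 2019 | 12 | 11.17 | 11.56 |
| 15 Nov 2018 | 15 Nov 2018 | 1 Jan 2019 | 47 | 10.02 | 11.56 |
| 25 Sep 2018 | 25 Sep 2018 | 1 Jan 2019 | 98 | 8.34 | 11.56 |
| 30 Jun 2018 | 30 Jun 2018 | 1 Jan 2019 | 185 | 5.49 | 11.56 |
| 10 Feb 2019 | 10 Feb 2019 | 10 Feb 2019 | 0 | 12.88 | 12.88 |

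The last row marks the limit of the problem: if last contact falls in the recorded year, the two rules agree.

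**3. Limit on schedule.** A contact 7 days late gives a gap of 3 × 30.4375 + 7 = 98.3 days, or 105.3 days if the previous contact was also 7 days early. The two rules cannot differ by more than that gap. After loss to follow-up there is no such limit.

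**4. A lost subject.** Last known alive 10 Jun 2018, death recorded as 2020.
- SAP rule: (146 + 1) / 30.4375 = 4.83 months.
- Alternative: (716 + 1) / 30.4375 = 23.56 months.

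Under the SAP rule this subject counts as dead for the 6, 9, 12 and 18-month OS rates, although the record shows survival past all four. With no other censoring, one such record lowers each rate by 1/144 = 0.7 percentage points in the platinum-refractory combination arm, or 1/72 = 1.4 points in the control arm.

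**5. Average error.** Let g be the gap in months from last contact to death, with last contact uniform over the calendar year. The SAP rule understates survival by g. With the 1 January bound:
- For g ≤ 12, the record crosses a year boundary with probability g/12 and the error then averages g/2; otherwise it stays g. Mean = g(1 − g/12) + (g/12)(g/2) = g − g²/24.
- For g > 12, every record crosses and the error averages 6 months.

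| Assumed gap (uniform) | SAP rule | Bounded rule | Crosses a year boundary |
|---|---|---|---|
| 0–3 months | 1.5 | 1.5 − 3/24 = 1.4 | 1.5/12 = 12.5% |
| 3–12 months | 7.5 | 7.5 − 63/24 = 4.9 | 7.5/12 = 62.5% |
| 6–36 months | 21.0 | 0.2 × (9 − 84/24) + 0.8 × 6 = 5.9 | 0.2 × 9/12 + 0.8 = 95% |

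The numerators 3, 63 and 84 are the mean of g² over 0–3, 3–12 and 6–12 months. Simulation under the same assumptions gave the same mean errors.

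**The case against.** The strongest case is that this hardly matters. On the contact schedule only about one such record in eight crosses a year boundary, and the average gain is 0.1 month. The large figures need a subject who is lost for a long time, later found to have died, and whose death is known only by year. The documents give no count of such records. SAP 5 and 7.5 confine testing to ORR in the platinum-refractory subgroup, so OS and PFS are only estimated, and the rule is the same in both blinded arms. All of this stands, and it limits the point to a minor one.

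The registry argument is also thinner than it looks. The stated purpose of the quoted search is updated contact information, though the sentence before it mentions vital status. Nothing says that registries return partial dates, and Protocol 3.7.2 tells sites to obtain the date of death. Year-only dates from tracing are plausible, not documented.

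One defence does not stand. The section opens permissively, saying that its conventions may apply, but the death-date rules are introduced as ones that will be used.

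A reader might go further and infer that dates of subsequent radiotherapy or surgery are misplaced in the same way, because the catch-all for other dates says "If only the day of the month is missing, the 15th of the month will be used to replace the missing day" and "If both the day and the month are missing, “July 1” will be used to replace the missing information" with no bound, and these dates can censor PFS or close the response window. The documents do not support that as a finding. SAP 8 names no rule for radiotherapy or surgery dates, the catch-all is only permissive, and medication dates go to an external specification that cannot be seen here. SAP 7.5.1.2 and 7.5.3.2 already plan ORR and PFS analyses that disregard subsequent therapy. A floor for such dates at the last study dose would also conflict with Protocol 3.5.3, which allows palliative radiotherapy for painful bone lesions while on study.

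**Conclusion.** The point holds in a narrow form. With the year known and the month missing, SAP 8 discards the year. Whenever the last known alive date falls in an earlier year, the death is dated too early, against both the record and the principle of the neighbouring day-missing rule. OS is affected directly. PFS is affected only when death is the event, with no earlier progression by central review and no earlier subsequent therapy that censors. DOR is affected only in responders whose response ends with death.

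The effect is negligible for subjects contacted on schedule. It can reach many months for a subject lost and later traced, but that size rests on the assumed gap, and the number of such records is unknown though probably small. The 21-month average should not be read as the expected bias in the trial's OS results; it describes one assumed kind of record. The primary ORR does not use the death date. DOR belongs to the primary objective but is described, not tested.

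**What to change.** In SAP 8, replace the rule for a missing month or year with:

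*If the day and month of death are missing but the year is known, the death date is the later of 1 January of that year and the last known alive date. The last known alive date is used alone only if the year is missing.*

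The rule for a wholly missing date can stay as it is.

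This extends the section's own day-missing rule by one step. It needs no new data, only a sentence in the SAP and a small change to the date-imputation code. It still places the death at the earliest date compatible with the record, so some downward bias remains: 5.9 months on average in the 6 to 36-month case, instead of 21.
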